3.2 Study Population

The study cohort consists of selected hospital district areas that have INR measurements available for AF patients using warfarin. See also [Sections 3.1](#) and [3.3](#).

3.2.1 Inclusion Criteria

Patients fulfilling the following criteria are included in the study:

- Patient has purchased warfarin (Anatomical Therapeutic Chemical classification (ATC) code B01AA03) between 01-Jan-2007 and 31-Dec-2009,
- Patient has at least one INR measurement available between 01-Jan-2007 and 31-Dec-2009, and
- Patient has a International Classification of Diseases (ICD-10 version 10) diagnosis code I48 for AF between 01-Jan-2005 and 31-Dec-2009.

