3 STUDY DESIGN

3.1 Overview of Study Design

The study with cohort design is conducted as a nationwide retrospective register-based linkage study using data obtained from the Finnish health care registers. The study population consists of all AF patients using warfarin with INR measurements in selected hospital district areas in Finland between 01-Jan-2007 and 3-Dec-2009.

Index date: Index date is defined as the date of first purchase of warfarin after 01-Jan-2007.

Follow-up period: Follow-up of the patients starts on the index date, and ends on 31-Dec-2011, at time of death or at time of emigration whichever occurs first.

History period: Treatment and comorbidity history is gathered from the period 01-Jan-2005 through 31-Dec-2006.

The key milestones of the study process are given below (Table 3.1-1). Note that the timelines are estimates only and are subject to change depending on the duration of the data permission processes and actual receipt of the data from the register holders.

Table 3.1-1: Study Timelines

Milestone	Anticipated date
Study protocol approved	4-Mar-2013
Registration in the ENCePP e-Register	30-Apr-2013
Ethics committee approval	30-Apr-2013
Data permit approvals	30-Jun-2013
Receipt of data from register holders	30-Sep-2013
Final study report	30-Dec-2013

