3.2.2 Exclusion Criteria

- Patients with permanent residence in Finland less than 12 months prior to index date.
- Patients with age below 18 years at index date.

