4 STATISTICAL ANALYSIS

4.1 Statistical Analysis Methods

Data management, tabulations, graphics, and statistical modeling in carried out with R language (<http://www.r-project.org>). R language is described more detailed in report "R: Regulatory

Compliance and Validation Issues: A Guidance Document for the Use of R in Regulated Clinical Trial Environments" (<http://www.r-project.org/doc/R-FDA.pdf>)

A separate statistical analysis plan (SAP) including detailed statistical analysis and outputs will be produced by EPID research prior to performing any analysis.

Study population: The study population will be described at baseline (start of follow-up) using by previous drug exposure and other covariates.

Study outcomes: All study outcomes will be summarized by drug exposure and other covariates.

Drug exposure: Drug exposure starts at date of purchase. The length of the exposure period is calculated as $DDD/dose \times 1.5$, where DDD (daily defined dose) is the total amount purchased and “dose” is the amount used daily (one for an average person). For the first purchase “dose=1” and for other purchases the “dose” is calculated from previous use by dividing the previous DDD with the time between the present and the previous purchase.

The impact of the multiplier 1.5 in the construction of drug exposure will be evaluated for the primary objectives in sensitivity analyses by using multiplier values 1.25, 1.5 and 2. We will also perform a sensitivity analysis for the primary objectives by including only those patients with at least two purchases of prescriptions within a clinically meaningful timeframe of 3 months after the index date.

INR levels: Daily INR levels are calculated:

- 1) As the previous recorded INR measurement
- 2) By linear interpolation between two consecutive INR measurements. If the gap between the measurements is more than 60 days the previous measurement is applied.

Daily INR estimates are categorized into levels: under 2.0, 2.0-3.0, over 3.0. In addition when appropriate a finer categorization is used: under 1.5, 1.5-2.0, 2.0-3.0, 3.0-4.0, 4.0-5.0, 5.0-9.0, and over 9.0. This finer categorization will be used only in the analysis of the primary objectives.

Time in therapeutic range (TTR): The INR target value for AF patients is 2.0-3.0. In addition for stroke, systemic thromboembolic events, and myocardial infarction INR target above 2.0 is considered and for bleeding events INR target under 3.0 is considered.

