4.1.1 Primary Objective

Objectives 1-3: Stratified incidence rates with 95% confidence intervals (CIs) will be estimated for each primary endpoint within the strata of the exposure variables (INR levels and TTR categories) and other covariates, including history of AF prior the index date.

The crude and adjusted hazard ratio (HR) estimates with 95% CIs and P-values will be estimated separately within the INR levels and TTR categories using the conventional Cox's proportional hazards model adjusting for other covariates. For INR the category 2.0–3.0 will be used as the reference category. Similarly for TTR the category $\geq 60\%$ of time will be used as the reference category.

The objectives will be evaluated separately for the prevalent warfarin user population and the new warfarin user population. The new warfarin user population consists of those patients who initiate warfarin treatment during the follow-up (01-Jan-2007 to 31-Dec-2009).

A further sensitivity analysis will be performed where the adjusted HRs are estimated stratifying by the history of AF prior to the index date.

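### Follow-up starts at the first warfarin purchase, but the AF code and INR test that qualify a patient may come up to three years later, which distorts the absolute event rates

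*Protocol*

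**What the plan says.** Protocol Section 3.1 fixes time zero: "Index date is defined as the date of first purchase of warfarin after 01-Jan-2007". It adds: "Follow-up of the patients starts on the index date, and ends on 31-Dec-2011, at time of death or at time of emigration whichever occurs first". Section 3.4.1 measures the time to every primary outcome from the same date.

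Section 3.2.1 sets three entry conditions:

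- a warfarin purchase ("code B01AA03) between 01-Jan-2007 and 31-Dec-2009");
- an INR test ("Patient has at least one INR measurement available between 01-Jan-2007 and 31-Dec-2009");
- an AF code ("diagnosis code I48 for AF between 01-Jan-2005 and 31-Dec-2009").

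Only the purchase is tied to the index date. The exclusions in Section 3.2.2 cover age and residence ("Patients with permanent residence in Finland less than 12 months prior to index date") and do not mention a late AF code or a late INR. No delayed entry is described, and Section 5 does not list the issue as a limitation.

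Two planned analyses bear on the point. Section 4.1.1 uses AF history before index as a stratifying covariate and says: "A further sensitivity analysis will be performed where the adjusted HRs are estimated stratifying by the history of AF prior to the index date". Section 4.1 plans a sensitivity analysis "including only those patients with at least two purchases of prescriptions within a clinically meaningful timeframe of 3 months after the index date".

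**The concern.** A patient who buys warfarin in January 2007 and is first coded I48, or first has an INR on file, in late 2009 is counted as at risk from January 2007. Had that patient died in 2008, he or she would not be in the study. Two things follow.

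- **Death.** The interval between index and qualification is death-free by construction. It adds person-time without deaths, so all-cause and cause-specific mortality, both primary outcomes, read too low.
- **Stroke, infarction and bleeding.** Diagnoses come from the care register, and the outcomes are hospitalisation and death codes. An outcome admission may be the occasion on which AF is first coded. That event then makes the patient eligible and is also counted after index, so these rates can read too high.

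Stratified incidence rates are a planned primary estimate in Section 4.1.1, so the harm falls on a headline result. The two-purchase sensitivity analysis has the same fault: patients who die before a second purchase are dropped, while the remaining patients' follow-up still starts at index.

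**Working it through.** **1. Longest permitted delay.** From 02-Jan-2007 to 31-Dec-2009 is 1,094 days (1,095 if a purchase on 01-Jan-2007 counts), about 3.0 years.

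**2. The plan's own size (Section 4.2).** 3,000,000 × 0.016 × 0.67 = 32,160, stated as 32,000. 32,000 × 3 years = 96,000 person-years. Both reproduce.

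**3. Mortality.** Assumed true rate: 6 per 100 person-years, the highest planning rate in Section 4.2 (the cited range for total death is 3.04 to 5.72). The share of late qualifiers p and the delay g are not in the protocol. I take p = 5% to 30%.

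Take an index date in January 2007, so 5 years are available, with constant hazard 0.06:

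- Mean follow-up if qualified at index: (1 − e^(−0.06×5))/0.06 = 4.32 years.
- Mean follow-up if qualified after g years: g + (1 − e^(−0.06×(5−g)))/0.06.
- Immortal share of person-time: p × g divided by the cohort's mean follow-up.
- Observed rate: 6 × (1 − immortal share).

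Long delay, g = 1.5 years (the mean if delays spread evenly to 31-Dec-2009):

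- Late qualifiers' follow-up: 1.5 + 3.157 = 4.657 years. Their rate: 6 × 3.157/4.657 = 4.1.
- p = 30%: 0.45/(0.3×4.657 + 0.7×4.32) = 0.45/4.421 = 10.2%; rate 5.39.
- p = 5%: 0.075/4.337 = 1.7%; rate 5.90.

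Short delay, p = 30%:

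- g = 90 days (0.246 years): 0.0738/4.338 = 1.7%; rate 5.90.
- g = 30 days (0.082 years): 0.0246/4.33 = 0.6%; rate 5.97.

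Simulation of the same cases agrees:

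| Delay and index date | Overall rate, p from 5% to 30% |
|---|---|
| Evenly spread to 31-Dec-2009, index January 2007 | 5.91 down to 5.41-5.45 |
| Evenly spread to 31-Dec-2009, index spread over 2007-2009 | about 5.9 down to 5.6 |
| Exponential, mean 90 days | about 6.0 down to 5.88 |
| Exponential, mean 30 days | 6.00 down to 5.97 |

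Starting the clock at qualification returns 6.0 in each case. A cruder sum using the protocol's 3-year mean follow-up with a 1.5-year mean delay gives 6 × (1 − 0.30×1.5/3) = 5.1. I do not rely on it: it pairs the delay of a January 2007 entrant with a shorter follow-up than that entrant would have.

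**4. Stroke, illustration only.** Expected events at 1.5 per 100: 96,000 × 0.015 = 1,440. Each 1% of 32,000 patients who enter through a post-index stroke admission adds 320 events, and 320/1,440 = 22%. If 5% of the cohort qualify late (1,600) and 5% of those enter through a stroke, the addition is 80 events, or 5.6%.

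**5. What reaches the INR comparisons.** Under Section 4.1 a daily INR is the previous recorded value or an interpolation between two values. Days before the first INR therefore have no level and largely drop out of the INR contrasts. Days between the first INR and a later I48 code do have a level and stay in.

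**The case against.** The strongest reply is that the protocol partly anticipates this. It recognises that some patients lack AF before index and plans hazard ratios stratified by AF history. That stands in part: the prior-AF stratum is free of the I48 problem. The main analysis is not, the no-history stratum keeps the problem in full, and nothing comparable deals with a late INR.

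A second reply is that pre-INR time hardly enters the INR contrasts. That also stands, but such time remains in follow-up as defined, and time from first INR to a later I48 is unaffected.

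A third is that the size may be negligible. If late codes cluster within weeks of the first purchase, it is: 5.97 to 6.00 against 6.0.

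A reader might infer more than the protocol supports:

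- **That the INR and TTR hazard ratios are biased in a known direction.** Pre-qualification time is not assigned to one INR group by design, and no calculation here gives a direction or size.
- **That stroke is overstated by 22%.** That figure only converts an arbitrary 1%. With 5% late qualifiers, it would require one in five of them (320 of 1,600) to have entered through a stroke.
- **That time before the first I48 belongs to patients on warfarin for another indication.** A first register code within 2005-2009 need not be the first AF diagnosis.

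**Conclusion.** The plan is wrong as written on its dates: eligibility may be established up to about 3 years after follow-up begins, and nothing in the protocol corrects for it. Absolute mortality rates are understated, and rates of stroke, infarction and bleeding can be overstated.

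For mortality, the understatement runs from negligible to about 10% (6.0 reading as 5.4). This rests on an assumed 5-30% of late qualifiers, delays between about a month and an even spread to the end of 2009, and a constant hazard. For stroke, the size depends on how many patients enter through an outcome admission, which the protocol does not allow one to estimate. The hazard ratios may also be biased, but their direction and size cannot be determined from the document. Confidence is high on the date structure and low on the size.

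**What to change.** - **Main analyses.** Start at-risk time at the latest of the first warfarin purchase in 2007-2009, the first I48 code and the first INR test (delayed entry). Do not count as outcomes any events on or before that entry date, including the admission that supplies the first I48.
- **First-90-day objective.** Keep time since warfarin initiation as the clock, with patients entering the risk set only once qualified.
- **Two-purchase sensitivity analysis.** Start at-risk time at the second purchase.
- **Secondary Objective 2.** Moving the start of follow-up changes neither the AF date nor the initiation date, so negative intervals would remain. Either restrict this analysis to patients with I48 on or before warfarin initiation, or give AF first coded after initiation its own category beside the three in Section 4.1.2.
- **Reporting.** State how many patients qualify after their first purchase and the distribution of the delay.

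The dates needed are already among the data requested in Section 3.3. The cost is some early person-time and early events, including in the first-90-day analysis and, for the second-purchase start, in that sensitivity analysis.

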3.2.2 Exclusion Criteria

- Patients with permanent residence in Finland less than 12 months prior to index date.
- Patients with age below 18 years at index date.

3.3 Data Source/Data Collection Process

The study timelines are presented in the picture below:

Figure 3.3-1: Study Timelines

[figure not shown]

Table 3.3-1: Study Registers

Register	Register Holder	Information obtained
National Prescription Register	Kela – The Social Insurance Institution of Finland	Drug purchases (ATC codes)
National Reimbursement Register	Kela	Reimbursement decisions 207 for chronic arrhythmias (for population characterization)
Finnish Care Register, HILMO	National Institute for Health and Welfare	Diagnoses (ICD10 codes) and date of diagnosis
National Causes of Death Register	Statistics Finland	Time of death and causes of death (ICD-10 codes)
Laboratory databases	HUSLAB + other hospital laboratories	INR measurements and other relevant laboratory values
Finnish Cancer Registry	National Institute for Health and Welfare	Cancer diagnosis (ICD-O-3 codes) and date of diagnosis
Population Register	Population Register Center	Places of domicile 12 months prior to and on index dates.
Social HILMO	National Institute for Health and Welfare	Information (dates) about institutionalization (other than hospitalization)

- Data will be requested from the registry holders ([Table 3.3-1](#)) based on the study protocol.
- Data permits will be requested from each registry holder based on the study protocol and ethical approval.
- Approval of Ethical Review Board of Hospital District of Helsinki and Uusimaa (HUS) will be requested to cover the nationwide study.
- This is a fully register-based study and patients will not be contacted in any phase of the study.
- Warfarin exposure will be defined by Kela, who then will convert the patient IDs to study IDs (SIDs). Kela will then send the IDs and the SIDs to other register holders: Statistics Finland, National Institute for Health and Welfare, Statistics Finland, Population Register Center, and central hospital laboratories included in the study.
- EPID Research will receive unidentifiable data including SIDs only. All patient data handled by the researchers are then anonymous which ensures full data protection of the patients.

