3.4.3 Other Covariates/Control Variables

- Reimbursement code 207
 - Yes/no
- Information about hospitalizations and institutionalization (other than hospitalization)

- dates
- will be taken into account when defining the discontinuation of warfarin treatment
- Laboratory parameters for anemia characterizations
 - Blood picture
 - ◆ Haemoglobin
 - decrement of 20 g/L
 - being under the reference value
 - See [Appendix 2](#) for details.
- Concomitant use of class D interactive drugs according to SFINX (Swedish, Finnish, INteraction X-referencing, see [Appendix 3, Table 3](#) for complete ATC listing)
 - Concomitant use during the warfarin treatment period assumed by the purchases and exposure (see definition for exposure in Section 4.1).
- Age*
- Gender*
- Hospital district
 - Helsinki, Turku, Tampere, Kuopio, Oulu, Jyväskylä
 - other possible central hospitals
- CHADS₂^{11 12}
- CHA₂DS₂-VASc^{11,12}
- Comorbidities (more in detail in [Appendix 4](#))
 - Hypertension*
 - Thyrotoxicosis
 - Cardiomyopathy
 - Congestive heart failure*
 - Diabetes*
 - Stroke*
 - Transient ischemic attack*
 - Vascular disease**
 - Cancer
 - Venous thromboembolism
 - *included in CHADS₂ score and in CHA₂DS₂-VASc score
 - **included in CHA₂DS₂-VASc score.

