5 STUDY LIMITATIONS/STRENGTHS

Finland has a well-developed population register system with tens of years of longitudinal follow-up data. The persons are identified in the registers with a unique personal identification number enabling linkage between different registers. These data has not been collected for study purposes, which may affect the quality of the data. However, these registers have been considered reliable for scientific research purposes.

Only those citizens that have been living in Finland for 12 months prior to index date will be included in the study.

No exact prescribed dosing information is available. Dosing is assumed based on the information of purchases and package sizes with defined daily doses (DDDs).

Coverage of the Prescription Register containing reimbursement information of all permanent residents of Finland is about 97%. Missing data includes relatively inexpensive packages which are not reimbursed. Fully reliable information on eg, acetylsalicylic acid use is then not available.

Medications used during hospitalizations are not available. However, based on the hospital care register the hospitalization periods can be taken into account to define gaps in the drug treatment periods.

No nationwide database about laboratory measurements is available. The laboratory data is then collected from separate local central laboratories. All laboratory values for particular patients may then not be available. Also changes in places of domicile may affect the follow-up of the patients. On the other hand, previous published surveys on the subject have not included INR follow-up to this extend.

To avoid selection bias, the cohort time (years 2007 to 2009) was chosen to avoid complication of patients switching from warfarin to newer anticoagulant medications eg, dabigatran.

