APPENDIX 3 ATCS INCLUDED IN THE STUDY

Possible changes in the ATC code during the study period are taken into account by Kela – The Social Insurance Institution of Finland.

B01AA03: warfarin

Antiarrhythmics:

Group C01B: antiarrhythmics, classes I and III (listed in detail in Table 1)

Group C07: beta blockers / class II antiarrhythmics (listed detail in [Table 2](#))

C08DB01: diltiazem (class IV antiarrhythmic)

C08DA01: verapamil (class IV antiarrhythmic)

C01EB10: adenosine (other type antiarrhythmic)

Table 1: C01B ANTIARRHYTHMICS, CLASS I AND III

C01BA Antiarrhythmics, class Ia	
C01BA01	quinidine
C01BA02	procainamide
C01BA03	disopyramide
C01BA04	sparteine
C01BA05	ajmaline
C01BA08	prajmaline
C01BA12	lorajmine
C01BA51	quinidine, combinations excl. psycholeptics
C01BA71	quinidine, combinations with psycholeptics
C01BB Antiarrhythmics, class Ib	
C01BB01	lidocaine
C01BB02	mexiletine
C01BB03	tocainide
C01BB04	aprindine
C01BC Antiarrhythmics, class Ic	
C01BC03	propafenone
C01BC04	flecainide
C01BC07	lorcainide
C01BC08	encainide
C01BD Antiarrhythmics, class III	
C01BD01	amiodarone
C01BD02	bretylum tosilate
C01BD03	bunaftine
C01BD04	dofetilide
C01BD05	ibutilide
C01BD06	tedisamil
C01BD07	dronedarone
C01BG Other antiarrhythmics, class I and III	
C01BG01	moracizine
C01BG07	cibenzoline
C01BG11	vernakalant

Table 2: C07A BETA BLOCKING AGENTS

C07AA Beta blocking agents, non-selective	
C07AA01	alprenolol
C07AA02	oxprenolol
C07AA03	pindolol
C07AA05	propranolol
C07AA06	timolol
C07AA07	sotalol
C07AA12	nadolol
C07AA14	mepindolol
C07AA15	carteolol
C07AA16	tertatolol
C07AA17	bopindolol
C07AA19	bupranolol
C07AA23	penbutolol
C07AA27	cloranolol
C07AA57	sotalol, combinations
C07AB Beta blocking agents, selective	
C07AB01	practolol
C07AB02	metoprolol
C07AB03	atenolol
C07AB04	acebutolol
C07AB05	betaxolol
C07AB06	bevantolol
C07AB07	bisoprolol
C07AB08	celiprolol
C07AB09	esmolol
C07AB10	epanolol
C07AB11	s-atenolol
C07AB12	nebivolol
C07AB13	talinolol
C07AB52	metoprolol, combinations
C07AB57	bisoprolol, combinations
C07AG Alpha and beta blocking agents	
C07AG01	labetalol
C07AG02	carvedilol
C07B BETA BLOCKING AGENTS AND THIAZIDES	
C07BA Beta blocking agents, non-selective, and thiazides	
C07BA02	oxprenolol and thiazides
C07BA05	propranolol and thiazides
C07BA06	timolol and thiazides
C07BA07	sotalol and thiazides
C07BA12	nadolol and thiazides
C07BA68	metipranolol and thiazides, combinations
C07BB Beta blocking agents, selective, and thiazides	
C07BB02	metoprolol and thiazides

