APPENDIX 4 COMORBIDITIES

Variable	Definition (ICD-10)
Hypertension	I10-I15
Thyreotoxicosis	E05
Cardiomyopathy	I420-I422, I429
Congestive heart failure	I50
Diabetes	E10-E14
Stroke	I63, I64, I693-I698
Transient ischemic attack*	G45
Vascular disease	I20-I25, I65-I66, I672, I70
Cancer	C00-C97, D00-D09
Pulmonary embolism	I26
Other venous thromboembolism	I80-183

ICD=International Statistical Classification of Diseases and Related Health Problems.

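### Hypertension, diabetes and heart failure are defined by care-register ICD-10 codes alone, although Kela purchase data are linked, so CHADS2 and CHA2DS2-VASc can be understated

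*Protocol*

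**What the plan says.** Protocol Section 3.4.3 lists CHADS2 and CHA2DS2-VASc among the other covariates. It marks hypertension, congestive heart failure and diabetes as "included in CHADS₂ score and in CHA₂DS₂-VASc score" and refers to Appendix 4 for the comorbidity definitions. Appendix 4 has one definition column, headed "Definition (ICD-10", and gives no drug or reimbursement criterion.

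Table 3.3-1 (Section 3.3) names the sources:

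- HILMO supplies "Diagnoses (ICD10 codes) and date of diagnosis".
- The National Prescription Register supplies "Drug purchases (ATC codes".
- The National Reimbursement Register supplies "Reimbursement decisions 207 for chronic arrhythmias (for population characterization".

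Section 5 describes the care register in hospital terms: "based on the hospital care register the hospitalization periods can be taken into account to define gaps in the drug treatment periods". The drug groups of interest are named in Section 3.4.2 and in the appendix titled "APPENDIX 3 ATCS INCLUDED IN THE STUDY".

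**The concern.** Hypertension and diabetes are often treated for years without a hospital contact at which they are coded. The plan links a register that would show such treatment through purchases, but does not use it for these conditions. A patient on treatment for both, with neither coded in HILMO, is recorded as having neither and loses two score components.

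Section 4.1.1 stratifies the primary incidence rates by other covariates and adjusts the Cox models for them. Misclassified patients would fall into low-score strata and raise the event rates there, and adjustment for established stroke risk factors would be only partial. Section 3.3 says that data are requested on the basis of the protocol, so the SAP cannot use drug groups or decisions that were never requested.

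**Working it through.** **1. Can any listed source other than HILMO supply these diagnoses in living patients?** No.

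- The Causes of Death Register gives codes at death only.
- The Cancer Registry gives ICD-O-3 codes for cancer.
- Social HILMO gives dates of institutional care.
- The reimbursement extract is limited to decision 207, for chronic arrhythmias.
- The laboratory tests in Appendix 2 include no measure of glycaemia.
- No primary-care diagnosis register is listed.

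**2. Do the named drug groups include treatment for these conditions?** Hardly. Appendix 3 covers warfarin, antiarrhythmics (C01B, the C07 group with its combinations, diltiazem, verapamil, adenosine) and SFINX class D interacting drugs. Section 3.4.2 adds heparins, clopidogrel, dipyridamole and prasugrel. Neither list has antidiabetic drugs, ACE inhibitors, angiotensin receptor blockers or stand-alone diuretics. The C07 group, diltiazem and verapamil do not separate hypertension from rate control in patients with AF.

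**3. Direction.** A missed code can only remove a component from the score, so this error runs downward.

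**4. Size of the score deficit.** The protocol gives no figure to reproduce and no prevalence or sensitivity, so every input here is assumed. Let p_H and p_D be the prevalences of hypertension and diabetes and s the code sensitivity, with one point per condition (the usual scoring, which the protocol does not spell out) and the two conditions independent.

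Mean deficit = (p_H + p_D)(1 − s). Share losing at least one point = 1 − [1 − p_H(1 − s)][1 − p_D(1 − s)].

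| p_H | p_D | s | Mean deficit | Share losing a point |
|---|---|---|---|---|
| 0.50 | 0.20 | 0.70 | 0.70 × 0.30 = 0.21 | 1 − 0.85 × 0.94 = 20% |
| 0.60 | 0.20 | 0.50 | 0.80 × 0.50 = 0.40 | 1 − 0.70 × 0.90 = 37% |
| 0.60 | 0.25 | 0.40 | 0.85 × 0.60 = 0.51 | 1 − 0.64 × 0.85 = 46% |

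With heart failure included and wider assumptions (hypertension/diabetes/heart failure 40/15/15% to 70/25/35%, sensitivity 0.9 down to 0.3), the deficit runs from 0.70 × 0.1 = 0.07 to 1.30 × 0.7 = 0.91 points.

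**5. What this could do to an INR hazard ratio.** Take hypertension alone, with true prevalence p1 at INR below 2.0 and p0 in the reference category, and outcome hazard ratio h. Among patients without a code the remaining prevalence is q = p(1 − s)/(1 − p·s), and the residual bias factor is [1 + q1(h − 1)]/[1 + q0(h − 1)]. With s = 0.5 and p0 = 0.50, q0 = 0.25/0.75 = 0.333.

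- p1 = 0.60, h = 1.5: q1 = 0.30/0.70 = 0.429; factor 1.214/1.167 = 1.04.
- p1 = 0.70, h = 2.0: q1 = 0.35/0.65 = 0.538; factor 1.538/1.333 = 1.15.
- p1 = p0: factor 1.00, no bias.

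These factors apply to code-negative patients only. If codes have no false positives, code-positive patients carry no such residual, so the overall bias is smaller. For scale, Section 4.2 sizes the study to detect relative risks of 1.10 to 1.20.

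**The case against.** The strongest reply is that code-based comorbidity is an internally consistent choice and that the amount of under-recording is unknown. The protocol does not say which visits HILMO records. The hospital description appears where hospital stays are used to define gaps in drug treatment. A reader might infer that patients managed in primary care do score too low. The documents support only that they can, if their condition is not coded in HILMO.

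Other limits also stand:

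- Every patient needs an I48 diagnosis between 2005 and 2009 (Section 3.2.1), so each has some coded contact at which comorbidity may also be recorded. That contact can fall after the 2005-2006 history period, so the protection is partial. The loss it then causes is due to the history window, a separate matter.
- A reader might infer that the scores stratify every incidence table and enter every primary Cox model. Secondary objective 2 (Section 4.1.2) stratifies by INR, TTR and time from AF diagnosis only. Section 4.1.1 says only that other covariates are adjusted for, and the scores are listed beside their own components, so the final model terms are not fixed here.
- Appendix 3 is not the complete drug list, since Section 3.4.2 names further codes and Table 3.3-1 states no restriction on purchases. Even so, neither list names the missing groups, and Appendix 4 has no rule that would use them.
- A reader might infer that the INR hazard ratios are biased. Daily INR categories let one patient contribute time to several levels, so an imbalance in comorbidity between categories cannot be presumed.
- The documents mention no reimbursement decision other than 207. Section 5 also says that inexpensive, non-reimbursed packages are missing from the Prescription Register, so purchases would be incomplete evidence too.

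These points limit size and scope. They do not change the fact that treated but uncoded patients are classed as free of the condition. Section 5 acknowledges register quality only in general terms and does not mention under-recorded comorbidity.

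**Conclusion.** The point holds as a weakness of design that should be corrected; the protocol does not contradict itself here. As written, Appendix 4 and Table 3.3-1 can only lower the hypertension, diabetes and heart failure components for patients who are treated but not coded, and adjustment for these risk factors in the primary analyses may be incomplete.

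Under the narrower assumptions (hypertension 50-60%, diabetes 20-25%, sensitivity 40-70%) mean CHADS2 is understated by about 0.2 to 0.5 points. None of those inputs is in the documents. Bias in the INR hazard ratios is conditional on comorbidity differing between INR categories; the 1.04 to 1.15 range illustrates assumed imbalances among code-negative patients and does not estimate the bias in this study. Confidence is medium.

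**What to change.** Before the data permits are requested:

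- Add to the Kela request antidiabetic purchases (ATC A10), antihypertensive groups not also used for AF rate control and, where the register holder has them, reimbursement decisions for hypertension, diabetes and heart failure.
- Amend Appendix 4 so that diabetes and hypertension are each defined as an ICD-10 code or Kela evidence before the index date. Do the same for heart failure if a reimbursement decision is available; otherwise keep I50.
- Do not count C07, diltiazem or verapamil alone as evidence of hypertension.
- Report the ICD-10-only definition as a sensitivity analysis, and state the remaining under-recording in Section 5.

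The cost is a slightly larger request to a register holder already supplying data, and some drug-based false positives for hypertension. Table 3.1-1 puts protocol approval at 4-Mar-2013 and permit approvals at 30-Jun-2013, so the change is cheapest before the permit applications go out.
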